## LIST OF ABBREVIATIONS AND GLOSSARY OF TERMS

Term	Definition
AE	adverse event
ALT (SGPT)	alanine aminotransferase (= serum glutamic pyruvic transaminase)
ATC	Anatomical Therapeutic Chemical
AST (SGOT)	aspartate aminotransferase (= serum glutamic oxaloacetic transaminase)
BoNT	botulinum neurotoxin
BoNT/A	botulinum neurotoxin serotype A
BoNT/E	botulinum neurotoxin serotype E
BP	blood pressure
BUN	blood urea nitrogen
CBL	change from baseline
CFR	Code of Federal Regulations
CMP	clinical monitoring plan
CRO	Contract Research Organization
DAS	digital abduction score
EB-001	botulinum neurotoxin serotype E drug product
ECG	electrocardiogram
eCRF	electronic case report form
ED50	effective dose to product 50% DAS effect
EDC	electronic data capture
EOS	end of study
ET	early termination
FDA	Food and Drug Administration
GCP	Good Clinical Practice
GGT	gamma-glutamyl transferase
GLP	Good Laboratory Practices
GMP	Good Manufacturing Practices
HBsAg	hepatitis B surface antigen
HC	heavy chain
HDL	high density lipoprotein
HEENT	head, eye, ear, nose, throat

Term	Definition
HIV	human immunodeficiency virus
HR	heart rate
HSA	human serum albumin
ICF	informed consent form
ICH	International Conference on Harmonization
ICH E6	International Conference on Harmonization Guidance for Industry, Good Clinical Practice: Consolidated Guidance
IM	Intramuscular
IRB	institutional review board
IUD	intrauterine device
LC	light chain
LDH	lactate dehydrogenase
LDL	low density lipoprotein
MCH	mean cell hemoglobin
MCHC	mean cell hemoglobin concentration
MCV	mean (red) cell volume
MedDRA	Medical Dictionary for Regulatory Activities
mITT	modified Intent to Treat
mL	Milliliter
mouse LD 50	lethal dose to 50% of mice after intraperitoneal injection
msec	millisecond
NA	not applicable
ng	nanogram
NOAEL	no observable adverse effects limit
OHRP	Office for Human Research Protections
PCV	packed cell volume
PI	principal investigator
POSAS	Patient and Observer Scar Assessment Scale
PR interval	time between the onset of atrial depolarization and the onset of ventricular depolarization
PRN	as-needed
RBC	red blood cell

Term	Definition
RDW	red (cell) distribution width
RR interval	time elapsed between two consecutive R-waves
QRS duration	the interval from the beginning of the Q wave to the termination of the S wave, representing the time for ventricular depolarization
QT interval	interval representing the time for both ventricular depolarization and repolarization to occur
QTc	corrected QT (interval)
QT cB interval	QTc interval using Bazett's correction (msec) = $QT/(RR)^{1/2}$ , where the QT interval is measured in msec and the RR interval is measured in seconds
QT cF interval	QTc interval using Fridericia's correction (msec) = $QT/(RR)^{1/3}$ , where the QT interval is measured in msec and the RR interval is measured in seconds
SAE	serious adverse event/experience
SAP	statistical analysis plan
SCARS	Scar Cosmesis Assessment and Rating Scale
SNAP	synaptosomal-associated protein
SOT	spread of toxin
SUSAR	suspected unexpected serious adverse reactions
RR interval	time elapsing between two consecutive R waves in the electrocardiogram. It is used to assess the ventricular rate.
TCA	trichloroacetic acid
TEAE	treatment emergent adverse event
µg	microgram
UP	unanticipated problem
US	United States
VAS	Visual Analog Scale
WBC	white blood cell (Leukocyte)
WHO	World Health Organization

## PROTOCOL SUMMARY

### **Study Number:**

EB001-SR201

### **Study Title:**

A Phase 2 Study to Evaluate Safety and Efficacy of EB-001 Injections in Facial Scar Reduction After Mohs Surgery

### **Investigational Drug Product:**

EB-001 (Botulinum Neurotoxin Serotype E, BoNT/E) for injection

### **Study Objectives:**

*Safety Objective:* To determine the safety and tolerability of single treatment of EB-001 when injected into forehead muscles underlying a surgical wound during Mohs surgery.

*Efficacy Objective:* To evaluate the efficacy of EB-001 intramuscular (IM) injection into the forehead muscles underlying the surgical wound in improving wound healing, and reducing scar formation.

### **Phase of Trial:**

Phase 2

### **Clinical Hypothesis:**

*Safety:* In patients undergoing Mohs surgery for skin lesions in the forehead area, a single treatment with EB-001 when injected into the muscles underlying the incision area will have an acceptable safety and tolerability profile.

*Efficacy:* In patients undergoing Mohs surgery for skin lesions in the forehead area, a single treatment with EB-001 when injected into the muscles underlying the incision area will improve wound healing and reduce scar formation.

### **Study Population:**

Healthy subjects 18 to 75 years of age, inclusive, undergoing dermatological surgical procedures to remove single skin lesions in the forehead.

### **Outcome Measures:**

#### **Safety Measures:**

- Incidence and severity of treatment emergent adverse events (TEAEs) and serious adverse events (SAEs)
- Focused neurologic examination for potential spread of toxin (SOT)
- Incidence of abnormal findings in laboratory tests, electrocardiogram (ECG), physical exam, and vital signs (pulse rate, respiratory rate and blood pressure)
- Urine pregnancy test for women of childbearing potential

Efficacy Measures:

- Scar assessment using a Visual Analog Scale (VAS)

[REDACTED]

Study Design:

This will be a randomized, placebo-controlled, single blind (to subject and study site personnel), parallel arm study with placebo or active treatment with IM injections. Subjects will be randomized to receive either a single dose (treatment) of EB-001 or placebo.

The study will be conducted at one center that specializes in dermatological surgical procedures. The study will include a visit for the surgical procedure (Day 1). Follow up visits will be scheduled at Days 2, 8, 30, and 90 (Table 1). The study will enroll approximately 12 subjects, randomly assigned to EB-001 or placebo in a 2:1 ratio for a total of 8 subjects in the EB-001 arm, and 4 subjects in the placebo arm (Figure 2).

Investigational (Study) Sites:

One dermatology site specialized in Mohs surgery.

[REDACTED]

[REDACTED]

Duration:

The expected duration for each subject participation is approximately 13 weeks from the day of surgery to the last visit.

Inclusion Criteria:

An individual must meet ALL the following criteria to participate in this study:

1. Between 18 and 75 years of age, inclusive
2. In good health, or with stable treated medical condition, as determined by the investigator.
3. Scheduled to undergo Mohs surgery to remove a single skin lesion in the forehead. This could be  
[REDACTED]
5. Women of non-childbearing potential must be postmenopausal (at least 12 consecutive months of amenorrhea)
6. Women of childbearing potential must not be pregnant, lactating, or planning to become pregnant during the study
7. Women of childbearing potential agreeing to use either
  - a. a highly effective method of contraception with failures rates less than 1% per year such as implant, intrauterine device (IUD), or sterilization from the day of dosing for 3 months (subjects who underwent sterilization must have initiated the procedure at least 3 months prior to the day of dosing) or
  - b. dual methods of contraception with overall failures rates less than 1% per year such as injectable, pill, patch, ring, and diaphragm from the day of dosing for 3 months (subjects using oral contraception must have initiated treatment at least 2 months prior to the day of dosing)
8. Willing and able to complete and comply with procedures, protocol requirements and instructions, which includes completion of all required visits
9. Willing and able to sign and date IRB-approved informed consent
10. Able to speak, read, and understand the language of the informed consent form (ICF) and study questionnaires

**Exclusion Criteria:**

An individual who meets ANY of the following criteria will be excluded from participation in this study:

1. Pregnant or breast feeding, or planning a pregnancy
2. Body weight less than 50 kg (110 pounds)
3. Reported use of any botulinum toxin of any serotype within last 6 months before study drug administration
4. Anticipated use of any botulinum toxin of any serotype during the study
5. Known hypersensitivity to any botulinum toxin serotype
6. Known allergy or sensitivity to any of the components of the study treatments, or any materials used in the study procedures
7. Aminoglycoside intake within 48 hours prior to or during surgery
8. Pre-existing disorders of the neuromuscular junction (myasthenia gravis, Eaton-Lambert syndrome, or amyotrophic lateral Sclerosis)

9. Any uncontrolled medical condition that in opinion of investigator, puts subject at undue safety risk
10. Any clinically significant psychiatric condition that, in opinion of investigator, may interfere with study assessments or protocol compliance
11. Any cosmetic procedure, laser resurfacing treatment, or retinoid therapy in the forehead area in the past 30 days before study drug administration
12. Any eyebrow or eyelid ptosis at baseline as determined by the Investigator
13. History of hypertrophic scars or keloid formation or other wound abnormalities as assessed by the investigator
14. History of alcohol or drug abuse in the last 3 years, based on investigator judgement

[REDACTED]

**Study Drug:**

[REDACTED]

[figure not shown]
**Placebo:**

Preservative free, sterile saline solution 0.9% Sodium Chloride Injection, USP.

**Dosage:**

[REDACTED]

Figure 1 Injection Sites

**Pre-Surgery Assessments:**

Written informed consent form (ICF), demographics, inclusion/exclusion criteria, medical history, physical and focused neurological examinations, height/weight, prior and concomitant medications, triplicate ECG, clinical laboratory tests (serum chemistry, lipids, hematology), immunogenicity sample collection, blood collection for human immunodeficiency virus (HIV) and hepatitis B and C, urine collection for drugs of abuse, and urine pregnancy test for premenopausal women.

**Safety Assessments:**

Adverse events, physical and focused neurologic examinations, prior and concomitant medications, triplicate ECG, vital signs, clinical laboratory tests, medical history, and urine pregnancy test.

**Efficacy Assessments**

Scar assessment using VAS, [REDACTED]

[REDACTED]

**Other Assessments**

Standardized facial photography will be performed to aid efficacy assessments.

**General Statistical Considerations:**

Analysis will be performed when all patients have completed the Day 90 visit or exited early from the study. The statistical analysis plan detailing all analyses will be signed off before the primary database lock.

For efficacy analysis, modified intent to treat (mITT) population including all randomized and treated patients with at least one post-injection efficacy assessment will be used. The safety analysis will be performed using safety population including all randomized and treated patients. All analysis will be performed on “as treated” basis.

For main safety analysis, incidence of all adverse events, TEAEs, and serious adverse events will be summarized for each treatment group. The efficacy variables are scar assessment multiple scales. The data will be summarized by descriptive statistics and 95% confidence interval (based on t-test) for treatment group will also be presented.

The planned sample size will be approximately 12 subjects (8 for EB-001 and 4 for placebo, Figure 2). For this pilot study, no formal sample size computations were made.

All statistical analysis will be descriptive summary statistics.

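### The visible plan names no EB-001 minus placebo estimate, although the trial is randomized against placebo to ask whether EB-001 reduces scarring

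*Combined protocol and SAP*

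**What the plan says.** The Study Design text of the protocol summary sets up a controlled comparison: "This will be a randomized, placebo-controlled, single blind (to subject and study site personnel), parallel arm study". Subjects are "randomly assigned to EB-001 or placebo in a 2:1 ratio for a total of 8 subjects in the EB-001 arm", with 4 on placebo. The efficacy part of Clinical Hypothesis is that a single EB-001 treatment "will improve wound healing and reduce scar formation", and the efficacy objective is framed in the same terms. Neither names placebo; the comparator comes from the design.

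General Statistical Considerations describes the efficacy analysis in one sentence: "The data will be summarized by descriptive statistics and 95% confidence interval (based on t-test) for treatment group will also be presented". It adds "All statistical analysis will be descriptive summary statistics" and, on size, "For this pilot study, no formal sample size computations were made". It refers all detailed analyses to a separate statistical analysis plan, to be signed before database lock. The text of that plan is not in the supplied document.

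No visible section names a between-arm difference, an interval for one, a test, a main scar scale or a main visit.

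**The concern.** Surgical wounds heal to some degree without treatment. Improvement and reduction therefore have meaning only relative to placebo, and supplying that reference is the purpose of the control arm. The sentence on efficacy attaches its 95% interval to a treatment group and not to the contrast between groups.

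If it is carried out that way, the report will hold one or two single-arm intervals and no stated estimate, with its uncertainty, of what EB-001 adds. A reader must then either derive the difference or set the two intervals side by side and judge by eye. The second habit is conservative in a way that is easy to underestimate at 8 v 4. If only the EB-001 arm receives an interval, the main efficacy display looks like that of an uncontrolled study.

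**Working it through.** **Inputs.** 8 EB-001 and 4 placebo subjects, and a 95% t-based interval (Study Design and General Statistical Considerations). The documents give no SD, so widths are in SD units. Normal data and a common SD are assumed unless stated otherwise.

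**The plan's own figure.** 12 × 2/3 = 8 and 12 × 1/3 = 4, so the split agrees with the 2:1 ratio. There is no power calculation to reproduce.

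**By-arm half-widths**, t(0.975, n−1)/√n:
- EB-001: 2.365/√8 = 0.84 SD
- Placebo: 3.182/√4 = 1.59 SD

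**Half-width for the difference**, with √(1/8 + 1/4) = 0.612:
- Pooled, 10 df: 2.228 × 0.612 = 1.36 SD
- Welch, equal SDs: df = (1/8 + 1/4)² / [(1/8)²/7 + (1/4)²/3] = 0.1406/0.02307 = 6.1, so 2.438 × 0.612 = 1.49 SD

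**Reading by overlap.** With equal sample SDs, the two arm intervals separate only when the means differ by more than 0.84 + 1.59 = 2.43 SD. The pooled interval for the difference excludes zero beyond 1.36 SD. Simulation of 200,000 trials per row (normal data, equal SDs, 8 v 4) gives:

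| True difference | Arm intervals do not overlap | Pooled difference interval excludes zero |
|---|---|---|
| 0 | 0.7% | 4.9% |
| 1 SD | 7.5% | 31.4% |
| 1.5 SD | 19.6% | 60.0% |
| 2 SD | 39.1% | 83.6% |

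**Precision once the contrast is added.** It remains low. With the pooled interval at two-sided 0.05 (an assumed level), 80% power needs a true difference of about 1.90 SD.

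**Pooled or Welch.** If the placebo SD is twice the EB-001 SD and there is no effect, the pooled interval wrongly excludes zero in about 12% of simulated trials, and Welch in about 6%. The Welch half-width is then 1.51 placebo SDs. If the EB-001 SD is twice the placebo SD, it is 1.93 placebo SDs.

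**Loss of one placebo subject (8 v 3).**
- √(1/8 + 1/3) = 0.677
- Pooled, 9 df: 2.262 × 0.677 = 1.53 SD
- Welch, equal SDs: df = (1/8 + 1/3)² / [(1/8)²/7 + (1/3)²/2] = 0.2101/0.05779 = 3.6, so 2.890 × 0.677 = 1.96 SD

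The degrees of freedom therefore cannot be fixed in advance.

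**The case against.** The strongest reply is that the contrast may already be planned. The protocol defers to a statistical analysis plan that cannot be seen here, and efficacy measures and assessments are partly blacked out. The wording "95% confidence interval (based on t-test) for treatment group will also be presented" is also open to three readings: the EB-001 arm, each arm, or a loosely described two-sample comparison. The mention of a t-test lends the third some support. Against it, the preceding sentence uses similar wording for by-arm safety summaries, and no difference is mentioned anywhere. The ambiguity stands, and it limits how firmly the gap can be stated. It does not remove the need to clarify the sentence.

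The second reply is that this is a declared descriptive pilot with no sample size calculation and no efficacy decision rule. That is right, and it rules out asking for a test or for power. It does not rule out a difference with an interval, which is estimation of the kind the plan already adopts.

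The third reply is that the plan proposes no overlap rule. That also stands. The overlap figures show what a tempting informal reading would cost; they do not measure an error in the plan. If both arms are reported with means, SDs and numbers, anyone can compute the difference.

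A reader might also infer from 1.59 against 1.36 SD that the placebo interval will be wider than the interval for the difference. That holds at a fixed SD. In simulated equal-SD trials it was wider than the pooled interval in only about 60%, and in about 13% when the EB-001 SD was twice the placebo SD.

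**Conclusion.** The point holds as a gap in the visible plan. The one efficacy interval described is most naturally by-arm or EB-001 only, and the quantity that the randomized design exists to estimate is not named. A direct 95% interval for it would have a half-width of about 1.4 to 1.5 SD, assuming normal data, equal SDs and all 8 v 4 subjects analysed. It would be wider with unequal SDs or with losses.

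A reader might infer that the trial never estimates EB-001 minus placebo, or that it cannot answer its efficacy question. The documents do not support either claim, because the detailed analysis plan is not supplied and the quoted sentence can be read in more than one way. No arithmetic in the plan is wrong. For a descriptive study of about 12 subjects this is an inexpensive improvement that should be made, not a defect that invalidates the trial.

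**What to change.** Amend the efficacy sentence in General Statistical Considerations, and carry it into the statistical analysis plan before sign-off, to this effect:

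- For each scar scale, present the EB-001 minus placebo difference in means with a two-sided 95% Welch t interval, with degrees of freedom taken from the subjects actually analysed.
- Name one scale and visit in advance as the main one, for example the VAS at Day 90, so that several unadjusted intervals do not compete to be the result.
- Give a Hodges-Lehmann shift with its rank-based interval as a sensitivity analysis, because the VAS is bounded and one arm has 4 subjects. An exact 95% interval exists at this size: there are 495 ways to choose 4 of 12, and 2/495 = 0.4% is below 5%.
- Keep arm means, SDs and by-arm intervals as descriptive support, and say explicitly that they are by-arm.
- Keep the analysis as estimation, with no formal test, and state the expected half-width of about 1.4 to 1.5 SD with its assumptions.

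The cost is a few lines of text and one extra table, with no added subjects or procedures. The downside is that the interval will be visibly wide, which is a fair picture of what 8 v 4 can show.

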**Figure 2 Study Design of EB001-SR201**
